Exclusion Criteria: The following characteristics exclude potential participants from being randomized into the study: DSM-IV* diagnosis of an uncontrolled psychiatric disorder with psychotic symptoms or cognitive impairment; if taking psychiatric medication, **NOT** on a stable dose for at least 30 days prior to randomization; any suicidal ideation in the past 7 days, plan or intent past 6 months, or suicide attempt past year; homicidal ideation with plan and intent in the past 30 days; PHQ-9 endorsement of hopelessness or self-harm/SI and/or sum score ≥ 19 on items 1-9; any use of prazosin or naltrexone past 30 days; currently taking disulfiram or acamprosate OR planning to take any of these medications (including prazosin or naltrexone) during the 8 weeks of the study; current moderate or greater level of substance use disorder (past 30 days) on any psychoactive substance other than alcohol, nicotine, or cannabis; current diagnosis of any opioid or amphetamine use disorder, OR use of any amphetamine or opioid-containing medications during the previous 30 days; UDA screen positive for amphetamine, opioids; significant acute or chronic medical illness including unstable angina, recent myocardial infarction, history of congestive heart failure, preexisting hypotension (sys <100) or orthostatic hypotension (sys drop of > 20 mmHq; after two minutes of standing, or any drop w/dizziness): insulin-dependent diabetes mellitus: chronic renal or hepatic failure; pancreatitis; Meniere's disease; benign positional vertigo or narcolepsy; liver enzymes aspartate aminotransferase (AST), cirrhosis, alanine aminotransferase (ALT), gamma glutamyl transferase (GGT), > 8 x the upper limit of normal or total bilirubin >2 mg/dL (in the absence of Gilbert's disease); allergy or previous adverse reaction to naltrexone, prazosin, quinazolines, or other α -1 adrenergic blockers or use of other α -1 adrenergic blocker; women who are pregnant, breastfeeding, or of childbearing potential and not using a contraceptive method judged by the investigator to be effective; legal involvement that could interfere with study participation including being court ordered for treatment; signs or symptoms of withdrawal at time of initial consent, or any participation in an experimental drug study or any addiction study past 30 days (See Appendix 1 for Initial Inclusion/Exclusion Checklist).

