Self-report Details. In addition, participants complete self-report measures on craving, drinking motives, and social networks. In addition, potential phenotypic moderators of interest will be examined, including family history of AUD, age of onset of drinking and AUD, drinking motives, depression, PTSD severity, anxiety sensitivity, emotional reactivity, disinhibition/impulsivity, and sensitivity to reward and punishment. They also complete the Stroop, another measure of impulsivity, which is administered by the RC or Study Clinician.

Medication Administration: Upon completion of the questionnaires the Study Clinician meets with the participant and orients him/her to the medication regimen. A two-week supply of the study medications loaded into a 14-day, 3-compartment Mediset is provided along with written instructions with visuals (i.e., pictures of the capsules) regarding dosing. Safety precautions regarding the medications are reviewed and participants are reminded to call the study telephone number should they experience any concerning side-effects or have any questions. The two-week prazosin titration schedule detailed in Table 1 is followed. Naltrexone does not require a titration period; participants are instructed to take the naltrexone/matched placebo capsule at the 9pm dosing time. Participants are given a pre-printed index-size card with study contact information and an alert that they could be taking naltrexone should they need emergency medical care involving pain medication (i.e., opiates).

Titration Schedule

ili alion Scriedule.				
Prazosin	9 AM	3 PM	9 PM	Naltrexone 9 PM
Dosing:				Dosing:
Days 1-2			1 mg	50mg
Days 3-4	1 mg	1 mg	1 mg	50mg
Days 5-7	2 mg	2 mg	2 mg	50mg
Day 8-10	2 mg	2 mg	8 mg	50mg
Day 11-14	4 mg	4 mg	8 mg	50mg
Day 15-42	4 mg	4 mg	8 mg	50mg

Study Clinician Safety and Comfort Call (Safety and Comfort Call #2): The Study Clinician calls each participant the day immediately following the initial dose of study medications to assess whether any concerning side effects were experienced, including any suicidal ideation.

Vital Signs and Adverse Events Checks (Visits 3-7; Safety Calls # 3 & 4):

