In-person Visits: To assure that participants are tolerating the study medications they are scheduled for five brief visits after the initial medication administration visit and before the final visit. Study days 12, 19, 29, 36, and 42 are the target (± 3 days) days for these in-person visits. At each of the in-person visits, sitting and orthostatic BP and HR are obtained. Participants are queried for adverse events using the open-ended question "How have you been feeling since you were last here?" Any elicited adverse events are recorded and rated for severity, duration, action taken, and relatedness to study medication. 20 mmHg drop in systolic BP accompanied by dizziness, lightheadedness or syncope at time of measurement or blood pressure systolic reading <100 with reported dizziness, lightheadedness or syncope at the time of measurement or between visits are considered unacceptable side effects and the titration is slowed or decreased to the last tolerated dosage or medication discontinued and study participation terminated as clinically appropriate. When the titration is adjusted, new study medications are requested from the pharmacy immediately and dispensed before the participant leaves.

In addition, participants complete a brief battery of measures to assess depression, anxiety, pain, and sleep and wake disturbance at each in-person visit. Participants are administered the PHQ-9 to screen for depression and suicidal ideation; the PHQ-9 was adapted for a one week timeframe.

Safety Calls: Study days 16 and 22 will be the target (± 3 days) days for the telephone calls 2 and 3. Participants are queried for adverse events using the open-ended question "How have you been feeling since we last saw you in the research clinic?" If safety concerns are apparent, participants are either be told to discontinue study medications or to adjust their dosing. An in-person study visit is scheduled as soon as possible in either case. The PHQ-9 suicide screen question is asked during each call with the timeframe adapted to cover since the participant last had contact with study staff.

Final Assessment and Craving Induction (Visit 8; Study day 42):

Final Visit Timing: Participants are scheduled to come back for their final visit approximately 7 weeks after their screening visit (Note: if scheduling difficulties arise there may be up to a two-week delay following the target end of the medication period in completing the final visit).

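### The in-person visit rule does not class a faint at home, first reported at a visit, as an unacceptable side effect when clinic systolic is 100 or above and there are no symptoms at measurement

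*Combined protocol and SAP*

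**What the plan says.** Under Vital Signs and Adverse Events Checks, In-person Visits, sitting and orthostatic pressures are taken at each visit. One sentence then defines an unacceptable side effect. It begins "20 mmHg drop in systolic BP accompanied by dizziness, lightheadedness or syncope at time of measurement or blood pressure systolic reading <100" and completes the second limb with "with reported dizziness, lightheadedness or syncope at the time of measurement or between visits are considered unacceptable side effects". When the definition is met, titration is slowed, the dose goes back to the last tolerated level, or medication and participation stop, as the clinical picture requires.

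Other text bears on the same event:

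- **Eliciting and recording.** Participants are asked "How have you been feeling since you were last here", and "Any elicited adverse events are recorded and rated for severity, duration, action taken, and relatedness to study medication". The schedule is "Study days 12, 19, 29, 36, and 42 are the target (± 3 days) days for these in-person visits".
- **Safety Calls** (target study days 16 and 22). "If safety concerns are apparent, participants are either be told to discontinue study medications or to adjust their dosing". A prompt in-person visit follows. No pressure reading is needed.
- **Medication Administration.** At dispensing, "participants are reminded to call the study telephone number should they experience any concerning side-effects or have any questions".
- **Study Instruments table.** The adverse events checklist is listed with vital signs as information for managing medication.
- **Exclusion Criteria.** At entry, the plan excludes "orthostatic hypotension (sys drop of > 20 mmHq; after two minutes of standing, or any drop w/dizziness".

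**The concern.** Prazosin is taken at home. By the titration schedule the 9 PM dose rises from 2 mg to 8 mg on medication day 8, and the daily total reaches 4 + 4 + 8 = 16 mg on day 11. A faint related to the evening dose would happen away from the clinic, and the clinic pressure may be taken long afterwards. The open question should bring the faint to light, yet whether it meets the written dose rule then depends on that later reading.

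The rule also ranks events oddly. A 20 mmHg drop with lightheadedness in the clinic qualifies. The same drop, without symptoms in the clinic but after an actual faint at home, does not qualify if systolic is 100 or above. At stake is whether a participant who has fainted continues at the same dose, or continues titrating, without a stated prompt to reconsider. With three sites and several types of study clinician, responses may also differ. This is a point about participant safety; it does not bear on the efficacy analysis.

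**Working it through.** The plan gives no figure to reproduce. The check is of the rule's logic.

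**1. The rule as written.** Let D = systolic drop of 20 mmHg or more in clinic, L = clinic systolic below 100, C = symptoms at measurement, H = symptoms between visits. Limb 1 carries its own timing (at measurement) and limb 2 carries a wider one, so:

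Rule = (D and C) or (L and (C or H))

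**2. The case in question.** Put C = no and H = yes. The first term vanishes and the rule reduces to L alone; the size of the drop no longer matters.

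**3. A more generous reading.** If the wider timing applied to both limbs, the rule would be (D or L) and (C or H). With C = no and H = yes this reduces to D or L.

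**4. Adding a standalone syncope trigger.** Any home faint then qualifies, whatever D and L are.

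| Drop ≥20 | Systolic <100 | As written | Wider timing on both limbs | Plus syncope trigger |
|---|---|---|---|---|
| yes | yes | met | met | met |
| yes | no | **not met** | met | met |
| no | yes | met | met | met |
| no | no | **not met** | **not met** | met |

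All rows are for a faint at home with no symptoms in clinic. They are patterns of the rule, with no frequencies attached, and do not give a proportion of participants.

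**5. Illustrative readings.**
- 130 sitting to 105 standing: 130 − 105 = 25, so D holds; both readings are at least 100, so L fails. Not met as written; met under the wider timing.
- 118 to 104: 118 − 104 = 14, so D fails; both readings are at least 100, so L fails. Not met under either reading; only the syncope trigger covers it.

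**6. A neighbouring case.** A home faint with symptoms in clinic, but no 20 mmHg drop and systolic of at least 100, also meets neither limb. The syncope trigger covers this too.

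**7. Entry against on-treatment.** The 130-to-105 reading exceeds the 20 mmHg entry limit, so if it were taken after two minutes of standing it would by itself bar enrolment. On treatment, the same reading plus a faint at home meets neither limb.

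**8. What the call rule covers (illustration).** Assume medication day 1 is study day 8. Medication day 8 is then study day 15, day 11 is study day 18 and day 42 is study day 49. The call windows are 16 ± 3 = 13 to 19 and 22 ± 3 = 19 to 25. The calls therefore fall around the dose increases, but none is scheduled after study day 25, and later home events would be picked up mainly at visits. The calendar is not fixed. Baseline Assessment allows up to an extra week, and if study days are counted from screening, medication day 8 becomes study day 22 and day 11 becomes study day 25.

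**The case against.** The strongest reply is that the visit sentence is not the whole safety system. The safety-call rule needs no pressure reading and leads directly to stopping or adjusting the dose. The Study Instruments table makes adverse events an input to medication management. Each elicited event is rated for relatedness and action taken. Participants are told to phone about side effects, and the research monitor has wide powers to protect participants. Nothing says the two limbs are the only grounds for a dose change. A reader might infer that the protocol has no written route from a faint at home to a dose change, or that clinicians may not act on one. The documents support neither inference.

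Much of this stands, and it confines the gap to a faint first reported at a visit. It does not close it. The call rule is discretionary, does not name syncope and is written for the scheduled calls. Recording the action taken documents a decision without prescribing one. The adverse events checklist is not reproduced, so whether it already prompts for syncope cannot be judged.

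Two further replies have force. An entry rule may reasonably be stricter than an on-treatment rule, so the comparison with the exclusion criterion is only supporting evidence. And a trigger for every faint would catch some not caused by prazosin: participants have alcohol use disorder, and two of the four arms take prazosin placebo. That is a fair objection to an unconditional trigger, and the fix below allows for it.

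**Conclusion.** The point holds in a limited form. The in-person visit rule counts between-visit symptoms only when clinic systolic is below 100. A faint at home, first reported at a visit with systolic of 100 or above and no symptoms at measurement, does not meet the written definition, even with a 20 mmHg drop. The other safeguards reduce the risk, but none names syncope or prescribes a response to it at a visit.

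This rests on the literal reading of the two limbs. On the more generous reading the gap narrows to participants whose clinic pressure meets neither threshold, but it remains.

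A reader might also take the table or the calendar as showing how often this would occur. They do not: the documents give no syncope rate, and the calendar depends on when medication starts. Because the size of the risk is unknown and clinicians remain free to act, the priority is low to moderate.

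**What to change.** 1. Apply the second limb's timing, which covers symptoms at measurement and between visits, to the first limb as well.
2. Add a trigger at visits: any syncope since last contact, regardless of the clinic reading, unless the Study Clinician documents a clear cause other than study medication. Name syncope as a safety concern on the calls.
3. Leave the choice of slowing, reducing or stopping to clinical judgement, as now.

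Step 1 alone is not enough, because a home faint followed by a normal clinic pressure is covered only by step 2. Dizziness or lightheadedness at home with a normal clinic pressure would remain a matter of judgement, which seems proportionate.

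The cost is about a sentence of protocol wording and a line on the visit and call forms, if the existing checklist does not already have one. The downside is possibly a few extra dose reductions, including in participants on prazosin placebo. The documents do not allow that number to be estimated; the exception for a documented other cause should limit it.

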Baseline Assessment: Approximately one week after the screening visit (Study Day 8) the RC or Study Clinician contacts each participant to inform her/him as to whether she/he continues to fit the study inclusion criteria. Note: If issues arise while attempting to contact participant, there may be up to an additional week between the initial screen and the baseline appointment. At the outset of this visit, blood pressure and suicidality are rescreened to ensure that participants are safe to start the study medications. Those that are eligible and wish to continue are asked to complete the Form-90 to evaluate drinking history over the past three months. They also complete the Script Preparation Form to provide details for the craving induction paradigm (see below). They also complete a battery of self-report measures as well as complete the two craving measures (Desire for Alcohol Questionnaire and Obsessive Compulsive Drinking Scale) again.

Form-90 Details. The RC or Study Clinician administers the Form-90 to ascertain drinking history over the last three months as well as involvement in various types of health care and mental health treatment.

Script Preparation Details. Participants complete the Script Preparation Form to provide details regarding two different recent situations that led to alcohol craving or actual use, including physiological and emotional reactions and specific information on the type of alcohol craved or consumed. One situation will have evoked anxiety, concern, or worry that led to craving or consumption, and the other will have involved craving or consumption meant to lead to or enhance positive emotional reactions in a situation or that pertain to desired effects of alcohol (e.g., feeling high, intoxicated, "good," etc.). These materials are used by study staff to write brief, personalized, imaginal craving inductions using a standard format that portrays each experience in the second person, present tense, and incorporates between five and seven different visceral and muscular reactions. The imaginal scene leads the person through the situation up to the acquisition of the alcohol and bringing the drink to her/his lips (but not consuming it). Each induction is 1 minute long (approximately 214 words) and is recorded in a neutral tone by someone other than the Study Clinician or RC for replay during the induction procedures at session 8

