Final Assessment: Participants will complete the CAPS, PHQ-9, PROMIS measures, Form-90 (adapted for the 7-week time interval), and the Stroop with the study RC or Study Clinician, as well as the same paper-and-pencil measures collected at Visit 2 and during the weekly visits. They then undergo the two craving inductions in counterbalanced order (see below). At the conclusion of the craving induction procedures, the Study Clinician checks the participants' vital signs and adverse events as per Visits 3-7, and questions will be answered about medication discontinuation. Level of craving is reassessed and if the participant indicates a strong desire to actually drink, the Study Clinician will work with him/her to identify alternatives or ways of drinking moderately. Laboratory evaluation of blood samples is repeated and again includes CBC, routine liver function tests, and routine serum chemistries. Specimens are sent to a lab in Minnesota, MedTox, for assessment of the alcohol biomarker phosphatidylethanol – Peth. The same blood draw procedures indicated above for Visit 1 are repeated at the final visit.

The portion of the visit with the Study Clinician may take place before the craving induction depending on scheduling and room availability. At the end of the appointment participants are thoroughly debriefed, and provided community or VA referrals for alcohol treatment. This portion of the visit may be conducted by either the RC or the Study Clinician.

Craving Induction Procedures: At approximately 1pm or later participants are oriented to the craving induction procedures by the study RC or Study Clinician. Participants are seated in a comfortable chair in a quiet, undecorated room and fitted with headphones. The craving inductions are presented in counterbalanced order. Immediately prior to the first induction participants rate their current craving using the abbreviated Desire for Alcohol Questionnaire (DAQ). Current positive and negative affect are also assessed with the PANAS. Participants are then be instructed to close their eyes and imagine that they are in the situation they are about to hear. Their personalized reward oriented or relief oriented craving scene is played over the headphones. At the end of the scene the participants imagine the scene for an additional three minutes following which they are asked to complete the same ratings as before. Participants then relax for 30 minutes with engaging but not

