Sensitivity to Reward/Punishment Scale	V1, V8	moderation (Aim 3)
PHQ-9 Depression	V1-V8	moderation (Aim 3); safety
Family History of AUD	V2	moderation (Aim 3)
Drinking Motives (Card Sort)	V2, V8	moderation (Aim 1)
Secondary Measures (Descriptive and/or Explorate	ory)	

AUDIT	V1	sample description		
Drinking Motives Questionnaire	V1, V8	sample description		
Obsessive Compulsive Drinking Scale	V1, V2, V8	sample description		
Form-90 (alcohol)	V2, V8	sample description and outcome		
Positive and Negative Mood States	IVR, V8	sample description		
Barrett Impulsivity Scale	V2, V8	sample description		
Stroop	V2, V8	sample description		
PROMIS Pain Impact	V2 – V8	sample description		
PROMIS Sleep quality	V2 – V8	sample description		
PROMIS Wake Disturbance	V2 – V8	sample description		
PROMIS General Distress; Anxiety	V2 – V8	sample description		
Important People Inventory	V2, V8	sample description and possible moderator		
Craving Induction Preparation				
Script Preparation Form	V2	provide details for craving inductions		
Medication Management / Safety Checks				
Adverse Events Checklist and Vital Signs	All	clinical data for medication management		
PHQ-9 Suicide item (#9)	All Phone Calls	safety		

Data Safety Monitor/Research Monitor

In accordance with DODI 3216.02, the research monitor, [name], has the authority to stop this research protocol in progress, remove individual human subjects from the research protocol, and take whatever steps are necessary to protect the safety and well-being of human subjects until the IRB can assess his report. [name] is responsible for promptly report his observations and findings to the IRB or other designated official. He may also have direct contact with study participants should it be necessary to evaluate their safety and to make recommendations for any needed care or actions.

Data Management

[name], M.S., a biostatistician from the University of Washington, will analyze the study data. Because [name] is not a VA employee, the study data will be temporarily transferred to her laptop for analysis. [name] will have the study data for one year. After one year, [name] will delete them from her laptop. All data transfers will be made using methods approved by the VA Privacy Office and Information Security Office.

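### Optional safety improvement: in-person visits screen suicidality over a fixed week, so a visit that slips within its window can leave days that no named suicidality item covers

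*Combined protocol and SAP*

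**What the plan says.** The protocol's section on vital signs and adverse event checks (Visits 3-7) uses two recall periods for the same safety question.

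- **In-person visits:** "Participants are administered the PHQ-9 to screen for depression and suicidal ideation; the PHQ-9 was adapted for a one week timeframe". The timing is: "Study days 12, 19, 29, 36, and 42 are the target (± 3 days) days for these in-person visits".
- **Safety calls:** targeted at Days 16 and 22, also with a 3-day window each way. The suicide item is asked "with the timeframe adapted to cover since the participant last had contact with study staff".
- **Final visit:** under Final Visit Timing, "there may be up to a two-week delay following the target end of the medication period in completing the final visit". Under Final Assessment, "Participants will complete the CAPS, PHQ-9, PROMIS measures, Form-90 (adapted for the 7-week time interval"). Form-90 has a stated recall period there and the PHQ-9 does not. The same sentence goes on to repeat the measures used at Visit 2 and at the weekly visits, which points to the one-week form.

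Other safeguards are in place. Recent suicidality is an exclusion criterion. At Visit 2, "blood pressure and suicidality are rescreened". A clinician asks about ideation by telephone the day after the first dose. Each in-person visit has an open adverse event question reaching back to the previous visit. Under Medication Administration, "participants are reminded to call the study telephone number should they experience any concerning side-effects or have any questions". The Study Instruments table gives the PHQ-9 the purpose "moderation (Aim 3); safety".

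**The concern.** A call closes the interval back to the previous contact, however long it was. An in-person visit does so only if the previous contact was at most 7 days earlier, and no text lengthens the look-back when it was not. The last planned call is on Day 22, so from then on screening rests on the one-week form.

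What is at stake is ideation that arose and resolved 8 to 13 days before a visit and that the participant does not volunteer. The protocol itself treats older suicidality as relevant: it excludes plan or intent within 6 months and an attempt within a year. An unasked episode of that age is therefore worth detecting and recording.

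**Working it through.** The plan gives no figure to reproduce; the check is calendar arithmetic.

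**Inputs.** Visits 3-7 on Days 12, 19, 29, 36 and 42; calls on Days 16 and 22; all ±3 days. First dose at Visit 2 on its target Day 8, so the clinician's call is on Day 9. Visit look-back 7 days; call look-back to the last contact.

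**Formula.** Uncovered days before a visit = max(0, gap − 7), where gap = visit day − day of the previous contact. Before a call the value is 0. The worst case takes the latest permitted visit and the earliest permitted previous contact, with contacts in planned order.

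| Visit | Previous contact | Gap on target | Uncovered | Worst gap | Uncovered |
|---|---|---|---|---|---|
| 3 | Call, Day 9 | 12 − 9 = 3 | 0 | 15 − 9 = 6 | 0 |
| 4 | Call, Day 16 | 19 − 16 = 3 | 0 | 22 − 13 = 9 | 2 |
| 5 | Call, Day 22 | 29 − 22 = 7 | 0 | 32 − 19 = 13 | 6 |
| 6 | Visit 5, Day 29 | 36 − 29 = 7 | 0 | 39 − 26 = 13 | 6 |
| 7 | Visit 6, Day 36 | 42 − 36 = 6 | 0 | 45 − 33 = 12 | 5 |

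**How much slippage is needed.** Shift the last call and Visits 5, 6 and 7 by every whole number of days within ±3: 7^4 = 2401 schedules.

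- A 6-day gap occurs in 98: 49 with the call on Day 19 and Visit 5 on Day 32, plus 49 with Visit 5 on Day 26 and Visit 6 on Day 39.
- At least one uncovered day occurs in 2108.
- With shifts of at most 1 day (3^4 = 81 schedules), 57 have at least one uncovered day and no single gap exceeds 2.

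These are counts of permitted schedules, not probabilities. Actual attendance is unknown.

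**Visit 8, assuming the one-week form.** Uncovered days = max(0, Visit 8 − Visit 7 − 7). The section heading places Visit 8 on Study Day 42, which is also Visit 7's target; the text places it about 7 weeks after screening. Forty-two days of medication from Study Day 8 end on Day 8 + 41 = 49. Two weeks late is then Day 42 + 14 = 56 or Day 49 + 14 = 63.

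| Visit 8 | Visit 7 on Day 39 | Day 42 | Day 45 |
|---|---|---|---|
| Day 49 (on time) | 3 | 0 | 0 |
| Day 56 | 10 | 7 | 4 |
| Day 63 | 17 | 14 | 11 |

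In the Day 63 row, only 10, 7 and 4 of those days fall on or before Day 49, the last planned medication day on that reading. If medication is read as ending on Study Day 42, the uncovered medication days in the two late rows are 3, 0 and 0.

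**After the fix.** A look-back to the last contact gives 0 uncovered days for any slippage.

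**The case against.** The strongest reply is that this is a preference. The planned schedule misses nothing. A fixed week suits roughly weekly visits, matches the 7-day entry criterion for ideation, and keeps PHQ-9 scores comparable across visits. Ongoing or recent ideation is still caught. An episode escapes only if it began and resolved more than 7 days before a visit, in an interval longer than 7 days, and went unmentioned when the participant was asked openly how they had been. The Study Instruments table also lists an adverse events checklist at all contacts; its items are not shown, so it may or may not name suicidality.

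Most of this stands, and it is why the point is optional. It does not remove the point: the open question does not name suicidality, the invitation to telephone relies on the participant, and the protocol's own call wording already solves the problem.

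A reader might infer more than the documents support:

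- **That the schedule has a built-in gap.** It does not; on target dates through Visit 7 the count is 0.
- **That a participant could plausibly accumulate 11 uncovered days (6 + 5) by Visit 7.** The windows allow it in 1 of the 2401 schedules, but only with Visits 5 and 6 on consecutive days (32 and 33). It should carry no weight.
- **That Visit 8 might use a 14-day PHQ-9.** Nothing in the text supports this.
- **That every visit needs a second item.** Visit 3 can never have an uncovered day, and elsewhere the need arises only after more than 7 days.

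**Conclusion.** The point holds as a cheap, optional improvement to patient safety. Through Visit 7 the uncovered time is 0 days on target dates. Within the permitted windows it is at most 2, 6, 6 and 5 days before Visits 4, 5, 6 and 7. The 6-day gaps need opposite window extremes, but the two 7-day intervals have no slack, so a one-day slip can open a one-day gap.

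The figures assume contacts in planned order and Visit 2 on Day 8. Uncovered means only that the plan as written shows no named suicidality item for those days. The Visit 8 figures rest further on the one-week form being used there and on which target day is meant, so no single number should be quoted for it.

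The gain is detection and recording of ideation between contacts. It gives no real-time protection, and the efficacy analyses are unaffected.

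**What to change.** At any of Visits 4 to 8 held more than 7 days after the last staff contact, also ask the suicide item with the look-back the calls already use. Leave the one-week PHQ-9, including its own suicide item, unchanged for scoring. Handle a positive answer to either item under the same safety procedure. In the Final Assessment section, state that the PHQ-9 at Visit 8 is the one-week form, if that is intended.

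The cost is one item at some visits, with a recall period that overlaps the PHQ-9 item, and a check of the date of last contact. The two answers may differ, which the common procedure covers. PHQ-9 scores and their comparability across visits do not change.
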